#### 3.8 Muscle biopsy

The baseline open muscle biopsy will be performed in one quadriceps muscle, or other appropriate muscle as determined by the PI. Open muscle biopsy of the quadriceps, or other muscle as determined by the PI (biopsy will be in the contralateral leg to the pre-treatment biopsy, unless otherwise determined by the PI), will be performed at 3 months post-infusion.

#### Every effort will be made to sample these same

muscles in all patients; however, in subjects (particularly older ambulant subjects) with limited quadriceps musculature, alternate muscle biopsy sites may be selected at the PIs discretion (including gastrocnemius or tibialis anterior muscles).

#### **Study Timeline** 3.9

#### Table 2. Schedule of Events Г

	(ILI-GT PROTOCOL) STUDY TIMELINE																	
Study Interval	Screening Pre Infusion Hespital Admission Vector Injection Inpatient Follow-Up (Outpatient)																	
Visit #	Visit 1 	Visit 2		Visit 3 	_	1	Visit 4	Visit 5	Visit 6	Labs 	Visit 7	Labs 	Visit 8 	Labs 	Visit 9 	Visit 10 	Visit 11 	Visit 12 
Study Procedures	Days to		Day -1	Day 0	Day 1	Day 2	Day 7	Day 14	Day 30	Day 45	Day 60	Day 75	Day 90	2 weeks post steroids	Day 180	Month 12	Month 18	Month 24
Informed consent 	X					~	~				~		~					
Medical History Physical exam	X X		x x	X X 	x	X X	X X	x	x x		x x		x x		x x	X X	x	X X
Adverse events	^		^	x	X	x	X	X	x		x		X		x	x	x	x
Concomitant medications	х		x	х	х	х	х	х	х		х		х		х	x	x	х
Vital signs	х		х	X 	Х	х	х	х	х		Х		х		х	х	х	х
Height	х												х		х	Х	х	х
Weight	x		х						х		х		х		x	x	x	х
ECHO	Ļ												x			v	, v	
ECHO FKG	X												X		X X	x	x	X
North Star Ambulatory																		
Assessment	х												х		х	х	х	х
Video recorded 6MWT	х												х		х	х	х	х
100 m walk/run	x						1	1	l	1	1	1	x		x	x	x	x
MVICT	х												х		х	х	х	х
PFTs/Spirometry	х														х	х	х	х
Anaesthesia		x		х			L				L		x		x	x		
CBC/Diff	х		х		х		х	х	х				х		х	х	х	х
AST/ALT	X		X		X		X	x	x	X	X	X	X	X	X	X	X	X
Serum GGT	х		x		х		х	х	х	х	х	х	х	Х	х	x	х	Х
Serum total protein/albumin	х				х		х	х	х				х		х	х	х	х
Serum Total bilirubin	X				X		X	X	X				X		X	X	х	X
Electrolytes	X X				x		X X	x	X X				X X		X X	x	X X	X X
Calcium Creatinine/BUN	x				x		X	x	x				X		x	x	x	X
Random Glucose	x				X		X	x	x				x		x	x	x	x
Alkaline Phosphatase	x				X		X	x	x				X		x	x	x	X
PT/PTT/INR	х		х		х		х	х	х				х		х	х	х	х
Amylase	х						х	х	х									
СК	х		х		х		Х		х				х		х	х	х	х
Cystatin C	х								х				х		х	х	х	х
Antibody testing Hep. B, C and HIV	х																	
Urinalysis	х				х		х	х	х		х		х		х	х	х	х
ELISA	х								х		х		х		х	х	х	х
ELISpot	х		х				х	х	х		х		х		х	х	х	х
Steroid Taper 			х	х	х	х	х	х	х	х	х	х	х					
Admit to Hospital				х														
Photograph injection site				x	х													
Ultrasound (Injection needle guide)				х														
Study agent administration		-		x			1	1		1	1		1					
Whole Blood Banking		х					1		х		х		1					
Urine Banking		х			Х	х	х	х	х		х							
			ges to the stud er multiple da	dy, parents will be r	e-conse	nted at th	neir next v	isit.										
					) and vis	its 8-10 v	vill be per	formed at	least 1 da	y precedi	ng the bio	psy.						
	
 
Muscle strength testing at baseline (days -45 to -1) and visits 8-10 will be performed at least 1 day preceding the biopsy.
 
An open muscle biopsy will be peformed on one leg at the baseline, and on the other leg at 3 months post gene transfer.
 
																	
	5 Pronbyl	actic prec	Inisolone/pre	dnisone taper begir	ns on Day	/-1 and is	stanered	according	to AST A	T and FI	ISnot resu	lts Antici	nate that	most subia	rts will be d	n nrednisol	one for up to	120 days
				st of the anesthesia					. to AST, AL	. 1, anu EL	Sportesu	its. Antici	pate tridt	most subje	.cs will be (	n preunisolo	me for up to	120 0035.
	7. Day 0 V	ital Signs	Heart rate, re	espiratory rate, puls	se oxime	try, temp	erature, a	nd blood j								nd at least e	very five min	utes during
				minutes post-infusi ontinue at post-trea												f/u visits wil	l be collecter	d at locally
				es include ALT, AST			33, 43, 73	, 3/10 5, 12	., 10, 0110 2		Post Sell	e aunarei	samples	scheduleu		., a visits Wil	. se concelet	actiocally

Note: There will be a flexibility of working days for each of the planned study visits including screening to adjust the schedule to any unanticipated event. The windows for each appointment are as follows:

- ٠
- ٠
- ٠
- Days 7 and  $14 \pm 2$  days Days 30  $\pm$  3 days Days 60 and 90  $\pm$  7 days Day 180, and Months 12, 18 and 24  $\pm$  14 days •

#### 3.10 Long-Term Monitoring

We will follow the most recent FDA guidelines with regard to long-term subject follow up after gene transfer. As discussed and based on prior experience with rAAV or transgene, there is a very low probability of gene transfer-related delayed adverse events. We will, however, evaluate short-term safety over a two-year period that incorporates the active phase of the protocol. Following the active two-year follow-up phase of the study, subjects will then be asked to transfer to a monitoring program where data will continue to be collected from annual visits with their standard care physician.

If newly identified risks are associated with our product, or if the subjects suffer any adverse events during this period, we will initiate a long-term follow-up according to the FDA guidelines. We will, of course, notify CBER if there is any indication of need to extend follow-up period. All subjects will be provided with written instructions on how to contact the Principal Investigator or study coordinator if they experience any serious adverse event that they consider possibly related to study treatment or study participation. This information will also be included in the Informed Consent document. All subjects will be instructed to notify the Principal Investigator of a change of address or contact information.

However, if significant findings become available that might increase the risk of the subjects or might affect their decision to remain in the study, then information will be made available as soon as it is available.

At the time of death, no matter what the cause, permission for an autopsy will be requested of their families. Subjects will be asked to advise their families of this request and of its scientific and medical importance.

#### 3.11 Outcome Measures

The intravascular limb infusion for gene therapy (ILI-GT) stage of the study is proposed as a phase I/II clinical trial inclusive of safety and efficacy outcome measures.

- A. Safety is the primary outcome for this clinical gene transfer trial. Stopping criteria are based on development of unacceptable toxicity defined as the occurrence of **two or more** unanticipated Grade III or higher treatment-related toxicities.
- B. Efficacy outcome measures: Muscle biopsy analysis for safety and transgene expression will be studied using multiple serial sections.
  - i. Expression of GALGT2 as demonstrated by immunofluorescent staining with anti-CT epitope antibodies or WFA lectin in muscle biopsy sections
  - ii. GALGT2 protein expression quantified by western blot and assessed by densitometry in muscle biopsy tissue

For each of these measures, statistical analysis based on differences between pre- and post-gene transfer muscle specimens will be analyzed using a paired t test (p < 0.05). Sections and western blots will be prepared by a single technician, who will blind the sample identifier; images will be obtained and expression assessed by another technician blinded to the sample time point.

- C. Exploratory functional outcome measures will be performed on the schedule as described.
  - i. The 6 minute walk test (6MWT), with either stabilization or a statistically significant change in distance walked on the 6MWT at 6 or 12 months after injection to be considered evidence of a positive result.
  - ii. Strength and functional testing will be performed at baseline and at days 90,180, and at months 12, 18 and 24. This will include the 6MWT distance as the primary functional variable. The maximum voluntary isometric contraction testing (MVICT), which will provide the force generated by the muscles of knee extension and knee flexion, will be an exploratory measure, as will the 100 meter walk time and the NSAA.

#### 3.12 Statistical Analysis

Measure of the 100 meter walk/run and MVICT of lower limb muscles will be analyzed by paired t-tests with a significance level of p = 0.05.

ALL data will be shared with the DSMB as gathered for each study subject. Any adverse events will be fully discussed with the DSMB and reported to the FDA.

## 4.0 ADVERSE EVENT REPORTING

In reporting adverse events, we will follow the final regulations issued by the Food and Drug Administration addressing the safety reporting requirements for investigational new drug applications (INDs) found in 21 CFR part 312 and for bioavailability and bioequivalence studies found in 21 CFR part 320. "Safety Reporting Requirements for INDs and BA/BE Studies".

http://www.fda.gov/downloads/Drugs/GuidanceComplianceRegulatoryInformation/Guidances/ UCM227351.pdf

#### 4.1 Classification of Adverse Events:

The classification for adverse events will follow NIH guidelines outlined in Common Terminology Criteria for Adverse Events v4.0 (CTCAE; published May 28, 2009), which includes:

**Grade 1** Mild; asymptomatic or mild symptoms; clinical or diagnostic observations only; intervention not indicated.

Grade 2 Moderate; minimal, local or noninvasive intervention indicated; limiting ageappropriate instrumental ADL.

**Grade 3** Severe or medically significant but not immediately life-threatening; hospitalization or prolongation of hospitalization indicated; disabling; limiting self-care ADL.

Grade 4 Life-threatening consequences; urgent intervention indicated.

Grade 5 Death related to AE.

A Semi-colon indicates 'or' within the description of the grade.

#### 4.2 Dose limiting toxicity (DLT)

Study enrollment will be halted by the investigators when any subject experiences two or more **Grade 3**, **or higher** adverse event toxicity that are unanticipated and **possibly**, **probably**, **or definitely related** to the study drug. The event will then be reviewed by the Data Safety Monitoring Board (DSMB) before making a determination to continue enrollment as described in Section 4.5 Dose Escalation.

Laboratory tests with values within the clinically significant range will be repeated during the same visit whenever possible (refer to Table 1 for a complete list of clinically significant range values). If the test result returns after the subject leaves the clinic, they will be immediately contacted. For local residents, they will be asked to return to the outpatient clinic for a repeat test. For non-local residents, arrangements will be made to have the blood test redrawn in a laboratory close to home or by their primary care physician.

We will

obtain copies of repeat laboratory tests and any relevant medical records that will be added to the subject's research chart.

The PI will fulfill the reporting responsibilities under 21 CFR 312.32(c), to notify FDA in an IND safety report of potentially serious risks, as soon as possible, but no later than 15 calendar days after the investigator receives the safety information and determines that the information

qualifies for reporting. The investigator will confer with the DSMB and FDA before continuing to enroll.

#### 4.3 Stopping/Discontinuation Rules

An independent Data Safety Monitoring Board (DSMB) will be established by the funding agency including a safety monitor for the study. Safety data will be monitored on a continual basis throughout the trial. The DSMB can recommend early termination of the trial for reasons of safety. Study enrollment will be halted by the investigators when any subject experiences two or more Grade 3 or higher adverse events that are **unanticipated** and **possibly**, **probably**, or **definitely related** to the study drug. This will include any subject death, important clinical laboratory finding, or any severe local complication in the injected area related to administration of the study agent. If after review by the DSMB the decision is made to continue, the study will proceed according to Section 4.5 (Dose Escalation) of this protocol.

#### 4.4 Expected Adverse Events Related to Disease Progression

Adverse events determined to be due to the underlying disease progression will be recorded but will not be subject to the expedited reporting requirements outlined in Section 5.0. All AEs related to the disease and unrelated to the gene therapy administration will be reported annually to the FDA, NIH/OBA and IRB.

#### 4.6 Dose Escalation

There will be at least 4-6 weeks between dosing of subjects within a cohort. The allowance of four weeks between dosing of subjects provides time for an internal review of the safety analysis from five time points (days 1, 2, 7, 14 and 30) prior to dosing of the next subject and time for review of the safety analysis of all the subjects within a cohort by the investigators and the DSMB. The 30-day post-injection data from one subject in the first cohort will be reviewed and discussed with the DSMB prior to dose escalation to the higher dose cohort. Dose escalation will be based on dose-limiting toxicity (DLT).

The investigators will confer with the IRB, and DSMB on all Grade 3 or higher adverse events that are possibly, probably, or definitely related to the study agent before continuing enrollment. Based on the outcome of the safety and efficacy analysis at the end of each cohort decisions will be made to proceed with dose escalation for the following cohort.

## 5.0 ADVERSE EVENT MONITORING

#### 5.1 Definition of an Adverse Event

As stated above, this protocol will follow the final regulations issued by the Food and Drug Administration addressing the safety reporting requirements for investigational new drug applications (INDs) found in 21 CFR part 312 and for bioavailability and bioequivalence studies found in 21 CFR part 320. "Safety Reporting Requirements for INDs and BA/BE Studies".

http://www.fda.gov/downloads/Drugs/GuidanceComplianceRegulatoryInformation/Guidances/ UCM227351.pdf

Adverse Events will be collected throughout the study from enrollment to last follow up visit.

Adverse Event (AE): Adverse event means any untoward medical occurrence associated with the use of a drug in humans, whether or not considered drug related.

Adverse events will be graded by the investigator accordingly: 1 = mild, 2 = moderate, 3 = severe, 4 = life threatening or debilitating, and 5 = fatal as indicated above in section 7.5.Association or relatedness to the study agent, study procedures and the subject's pre-existing disease will be graded as follows: 5 = unrelated, 4 = unlikely, 3 = possibly, 2 = probably, and 1 = definitely related.

Adverse reaction: An adverse reaction means any adverse event caused by a drug. Adverse reactions are a subset of all suspected adverse reactions for which there is reason to conclude that the drug caused the event.

**Suspected adverse reaction (21 CFR 312.32(a))** Suspected adverse reaction means any adverse event for which there is a reasonable possibility that the drug caused the adverse event. For the purposes of IND safety reporting, 'reasonable possibility' means there is evidence to suggest a causal relationship between the drug and the adverse event. A suspected adverse reaction implies a lesser degree of certainty about causality than adverse reaction, which means any adverse event caused by a drug.

#### 5.2 Serious adverse event (SAE)

An adverse event or suspected adverse reaction is considered "serious" if, in the view of either the investigator or funding agency, it results in any of the following outcomes: Death, a lifethreatening adverse event, inpatient hospitalization or prolongation of existing hospitalization, a persistent or significant incapacity or substantial disruption of the ability to conduct normal life functions, or a congenital anomaly/birth defect. Important medical events that may not result in death, be life-threatening, or require hospitalization may be considered serious when, based upon appropriate medical judgment, they may jeopardize the subject and may require medical or surgical intervention to prevent one of the outcomes listed in this definition. Examples of such medical events include allergic bronchospasm requiring intensive treatment in an emergency room or at home, blood dyscrasias or convulsions that do not result in inpatient hospitalization, or the development of drug dependency or drug abuse.

To reiterate, an SAE is an event in categories 3, 4, and 5.

- **Category 3:** Severe adverse event; inability to carry on normal activities; required professional medical attention
- **Category 4:** Life-threatening or permanently disabling adverse event
- Category 5: Fatal adverse event

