#### 5.5 Safety Reporting

The investigator or his designee will report all serious and unexpected adverse events to the IRB, NIH OBA, and DSMB according to regulatory requirements described as follows:

- DSMB and OBA/IRB: All Serious Adverse Events (SAEs) and Dose Limiting Toxicities (DLTs) will be reported to the DSMB and NIAMS, through KAI, and the IRB within 48 hours of notification, regardless of expectedness, relatedness, or if they meet the definition for unanticipated problems to the clinical trial
- **FDA/NIH OBA/IRB:** Any serious adverse event that is fatal or life-threatening, that is unexpected, and associated with the use of the gene transfer product will be reported by the study investigator concurrently to the **FDA/NIH** and the **OBA/IRB** as soon as possible, but not later than 7 calendar days after the funding agency's initial receipt of the information.

Serious adverse events that are unexpected and associated with the use of the gene transfer product, but are not fatal or life-threatening, will be reported concurrently to the **FDA/NIH OBA/IRB** as soon as possible, but not later than 15 calendar days after the funding agency's initial receipt of the information. Changes in this schedule will be permitted only where, under the **FDA IND** regulations [21 CFR 312(c) (3)], changes in this reporting schedule have been approved by the FDA and are reflected in the protocol.

If, after further evaluation, an adverse event initially considered not to be associated with the use of the gene transfer product is subsequently determined to be associated, then the event will be reported concurrently to the **FDA/NIH OBA/IRB** as soon as possible, but in no case later than **15 calendar** days after the determination is made.

Relevant additional clinical and laboratory data will become available following the initial serious adverse event report. Relevant follow-up information to an IND safety report will be submitted concurrently to the FDA/NIH OBA/IRB and the DSMB as soon as the information is available and will be identified as such, i.e., "Follow-up IND Safety Report." If a serious adverse event occurs after the end of a clinical trial and is determined to be associated with the use of the gene transfer product, that event will be reported concurrently to the FDA/NIH OBA/IRB and the DSMB within 15 calendar days of the determination.

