Any finding from tests in laboratory animals that suggests a significant risk for human research participants including reports of mutagenicity, teratogenicity, or carcinogenicity will be reported to FDA/NIH OBA/IRB and the DSMB as soon as possible to the , but not later than 15 calendar days after initial receipt of the information.

Should a serious adverse event deemed possibly, probably or definitely related to the study agent occur during administration, the study agent will be discontinued, appropriate treatment will be given under medical supervision and the subject will be examined as frequently as necessary thereafter until symptoms cease or stabilize.

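### Section 5.2 gives two SAE definitions that do not agree, so SAE reporting, SAE listings and the SAE trigger during administration are ambiguous

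*Combined protocol and SAP*

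**What the plan says.** Section 5.2 opens with a definition by outcome. An event is serious if "it results in any of the following outcomes", and the list covers death, threat to life, birth defect and "inpatient hospitalization or prolongation of existing hospitalization, a persistent or significant incapacity or substantial disruption of the ability to conduct normal life functions". An event with none of these may still be called serious on medical judgment.

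The section closes differently: "To reiterate, an SAE is an event in categories 3, 4, and 5". Category 3 is then described as "Severe adverse event; inability to carry on normal activities; required professional medical attention", category 4 as a threat to life or permanent disability, and category 5 as fatal.

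Severity is also described in two other places. Section 4.1 adopts CTCAE v4.0, where grade 3 begins "Severe or medically significant but not immediately life-threatening". It counts an indicated hospital stay, or a longer one, among the alternatives, and says that semicolons in the grades mean *or*. Section 5.1 uses the scale "1 = mild, 2 = moderate, 3 = severe, 4 = life threatening or debilitating, and 5 = fatal" and points for it to a section 7.5 that does not exist; section 7 is the reference list.

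SAE status is used in these places:

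- Section 5.4: electronic reports to NIH OBA.
- Section 5.5: "All Serious Adverse Events (SAEs) and Dose Limiting Toxicities (DLTs) will be reported to the DSMB", NIAMS and the IRB within 48 hours, whatever the expectedness or relatedness. The 7-day and 15-day reports follow.
- End of section 5.5: "Should a serious adverse event deemed possibly, probably or definitely related to the study agent occur during administration, the study agent will be discontinued".
- Section 6.2: annual summaries of SAEs.
- Section 6.3.2: a DSMB listing of SAEs, separate from the summary of events by severity.

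**The concern.** Seriousness (what the event led to) and severity (how intense it was) are different attributes. Section 5.2 defines the first, then replaces it with the second while presenting the change as a repetition. Two investigators who both follow the section faithfully could classify the same event differently.

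The error can go either way. If the category rule is applied, a lower-grade event with a serious outcome may miss the 48-hour clock, while severe events with no serious outcome enter the SAE listing. The listing then says little beyond what the severity table already says. The DLT and halting rules look only at grade, so the outcome-based SAE definition is the main expedited route for a lower-grade event with a serious outcome.

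**Working it through.** No arithmetic applies. The plan states no figure that depends on the SAE definition, so the check compares the two sets of events and traces where each is used.

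**Step 1. Compare the sets.** Section 5.2 does not say how to read the semicolons in category 3, so both readings are shown. The last column also covers use of the section 5.1 grades.

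| Event | SAE by outcome | SAE by category, semicolons as *or* | SAE by category, semicolons as *and*, or 5.1 grade |
|---|---|---|---|
| Fatal or life-threatening | Yes | Yes | Yes |
| Severe, professionally attended, no listed outcome, not judged medically important | No | Yes | Yes on the 5.1 grade; on *and*, only if normal activities were also impossible |
| Moderate, professionally attended, no listed outcome, not judged medically important | No | Yes | No |
| Graded moderate on the 5.1 scale, but prolongs the hospital stay | Yes | Yes | No |
| Graded moderate, judged medically important | Yes | Yes if professionally attended | No |

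Every category column departs from the outcome column somewhere. With *or*, the category set is much broader and takes in nearly all outcome-based SAEs, so the mismatch is mostly over-inclusion. On the section 5.1 grades the mismatch clearly runs both ways. With *and* it can also run both ways, although an event that stops normal activities may often count as a disruption of normal life functions and so be serious by outcome too.

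**Step 2. Apply the section 4.1 scale.** Under CTCAE v4.0 as quoted there, an event for which a longer stay is indicated is already grade 3. On that scale both rules capture the prolonged-stay event. Some medically important events would reach grade 3 as well, since that grade includes medically significant events. Severe events with no listed outcome remain SAEs by category only.

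**Step 3. Trace what depends on SAE status.**

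- The 48-hour report (5.5) covers all SAEs, so its scope changes with the definition.
- The 15-day report (5.5) and the NIH OBA report (5.4) change for events that are also unexpected and associated with the product.
- The 7-day report is limited to fatal or life-threatening SAEs. These are in both sets, so it does not change.
- The annual summaries (6.2), the DSMB listing (6.3.2) and the trigger during administration (5.5) change.

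**Step 4. Trace what does not depend on it.** The stopping criterion in section 3.11 counts unanticipated, treatment-related toxicities of grade III or higher. The DLT rule (4.2), the halting rule (4.3) and the consultation on related grade 3 or higher events under Dose Escalation (4.6) are also grade-based. The abstract (2.1) lists laboratory, immunologic and symptom findings as safety endpoints and does not name SAEs. The paired t-tests concern biopsy and functional measures.

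**The case against.** The strongest case on the other side is that this is a wording slip with little effect. Sections 4.0, 5.1 and 5.4 bind reporting to federal regulations, and the full outcome definition stays in section 5.2. Section 3.12 gives the DSMB all data as gathered, and section 6.3.2 gives it every adverse event by participant and by severity. An event not labelled serious would still be visible before escalation. Extra SAE reports from the category rule err on the cautious side. For allergic reactions, section 3.6.4 has its own grade-based rule for ending the infusion.

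Much of this stands, and it limits the harm. It does not remove the contradiction. A general reference to regulations does not tell site staff which of two written rules to follow, and visibility in a later listing does not restore a 48-hour clock.

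A reader might also infer three stronger things that the documents do not support:

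- *That the primary safety outcome has two event sets.* The primary outcome is safety in general. The one event criterion attached to it is based on grade and is the same under either SAE definition.
- *That one reclassified event moves the SAE rate by 1/1 = 100 points in a cohort, or 1/2 = 50 points overall.* The arithmetic is right for one subject per cohort and two in all, but only if that subject has no other SAE. No proportion of subjects with an SAE is planned, and any yes/no variable would behave this way with two subjects.
- *That every moderate event prolonging the hospital stay would be missed.* Section 4.1 already puts an indicated longer stay at grade 3. Under-reporting arises mainly on the section 5.1 scale, on an *and* reading of category 3, or for lower-grade events judged medically important.

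**Conclusion.** The concern holds as an inconsistency in a reporting definition. Section 5.2 states two SAE rules that differ on every reading, and no text ranks them. The 48-hour and 15-day reports, the NIH OBA reports, the annual and DSMB SAE tabulations and the trigger during administration are therefore ambiguous. The 7-day reports, the grade-based stopping, DLT and halting criteria and all planned statistics are unaffected.

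The conclusion rests on reading the section 5.2 categories as a severity scale, which their wording and their match to the section 5.1 grades support. The direction and amount of misclassification depend on which level 3 wording the site applies and how it reads the semicolons, and the documents settle neither. The number of events affected cannot be estimated, because no event rate is given. The change should be made because the text is contradictory and cheap to correct, not because a result of the trial depends on it.

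**What to change.** 1. In section 5.2, keep one SAE definition for reporting and listings. Either delete the restating sentence, or relabel the category list as a severity scale and state that it does not determine seriousness.
2. In the eCRF, record seriousness (with the criterion met) and severity grade as separate fields for every event. Build the SAE listing from the first and the severity summary from the second.
3. Use one wording for level 3 across sections 4.1, 5.1 and 5.2, say how semicolons are read, and correct the reference to section 7.5.
4. Reconcile the trigger during administration at the end of section 5.5 with the definition adopted. Which events should trigger it is a clinical decision for the investigators and the DSMB, and I propose no rule.

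The cost is a short text amendment, submitted to the IRB as section 6.4 requires, and a small eCRF change. No visits, samples or additional data are needed.
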